9.1. Efficacy Assessments

Efficacy will be assessed via spirometry assessments, subsequent exacerbations of COPD, and patient-reported outcomes (PROs). PRO assessments carried out at study

visits will be completed as the first assessment in the visit schedule before spirometry or any other study procedure.

9.1.1. Spirometry Testing

Spirometry assessments will be obtained using spirometry equipment that meets or exceeds the minimal performance recommendations of the ATS [Miller, 2005]. All participating sites will use standardized spirometry equipment provided by an external vendor contracted by GSK.

All participants will perform lung function maneuvers to assess FEV₁, and FVC at each study visit. For each testing session, at least 3 valid spirometry efforts should be attempted (with no more than 8) using the ATS guidelines [Miller, 2005]. The highest FEV₁ from the valid forced expiratory curves for each testing session will be used.

Protocol-specified spirometry will be performed in the morning (i.e., initiated between 6:00AM and 12:00PM) during visits when clinic FEV₁ is performed as shown in the SoA (Section 2). In addition, protocol-specified clinic FEV₁ must be completed in accordance with the lifestyle restrictions as defined in Section 6.3.1- Section 6.3.5.

During Visits 2 through Visit 6, spirometry will be performed prior to administering double-blind study medication at two time points: pre-bronchodilator (albuterol [salbutamol]) and post-bronchodilator. Post-bronchodilator FEV₁ will be conducted approximately 10 to 30 minutes after the participant-administers 4 inhalations of albuterol (salbutamol) via MDI (i.e., total of 400 mcg) using a spacer/valved-holding chamber or via one nebulized treatment. It is anticipated that participants who are enrolled into the study will receive albuterol as part of the routine treatment of AECOPD during visit 2. In this instance, spirometry should be scheduled to coincide with this treatment to allow post-bronchodilator recordings to be measured. During Visits 6-9, spirometry will be performed prior to administering maintenance COPD medication(s) at two time points: pre-bronchodilator (albuterol [salbutamol]) and post-bronchodilator (as defined above).

Rescue albuterol [salbutamol] should be withheld for 4hrs prior to spirometry measurements, where possible. Usual daily COPD medications should be withheld on the morning of spirometry assessments, where possible.

Baseline Clinic Visit FEV₁ is defined as the post-bronchodilator FEV₁ performed at Visit 2.

Spirometry assessments should be made as close to the scheduled time points as possible. Where multiple assessments are scheduled at the same time point, the sequence of assessments should ideally be as shown below. However, during the Screening Visit (Visit 1) and/or the Randomization Visit (Visit 2), this order may be modified as needed, including instances where some or all of these procedures are performed as part of routine/urgent/emergency/inpatient hospitalized care.

1. Vital signs

2. 12-lead ECG
3. Blood sampling
4. Spirometry assessment

Details regarding the spirometric procedures are provided in the instruction manual provided by the external vendor.

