4. OBJECTIVES AND ENDPOINTS

Objectives	Endpoints

Primary
 
 To characterize the dose response of nemiralisib administered in addition to SoC compared with placebo and SoC in participants diagnosed with an acute moderate or severe exacerbation of COPD 	
 Change from baseline in Clinic Visit trough forced expiratory volume in one second (FEV₁) at Day 84 measured post-bronchodilator Baseline is defined as the post-bronchodilator FEV₁ measured prior to the first dose of double-blind study treatment on Day 1.

Secondary
 
 To characterize the dose response and efficacy of nemiralisib administered in addition to SoC compared with placebo and SoC in participants diagnosed with an acute moderate or severe exacerbation of COPD 	
 Rate of moderate and severe exacerbations over the 12-Week Treatment Period Time to next moderate/severe exacerbation following index exacerbation Change from baseline in Clinic Visit trough FEV₁ measured pre and post-bronchodilator at Days 14, 28, 56, and 84 (Day 84: post-bronchodilator is the primary endpoint; pre-bronchodilator is a secondary endpoint) and at hospital discharge (only for participants who are hospitalized for the index

Objectives	Endpoints

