
 To evaluate the treatment effect of nemiralisib in addition to SoC compared with placebo and SoC on symptoms indicative of an exacerbation and on health status using Patient-Reported Outcomes (PROs) in participants diagnosed with an acute moderate or severe exacerbation of COPD To evaluate the usage of rescue medication in participants diagnosed with an acute moderate or severe exacerbation of COPD 	
exacerbation)
 
 Change from hospital discharge in clinic visit trough FEV₁ measured pre- and post-bronchodilator at Days, 14, 28, 56, and 84 (in participants hospitalized for index exacerbation only) 
EXAcerbations of Chronic Pulmonary Disease Tool (EXACT-PRO)
 
 Proportion of participants achieving the EXACT definition of recovery from the index exacerbation by Days 14, 28, 56, and 84 Time to recovery from index exacerbation Severity of subsequent HCRU-defined exacerbation(s) defined by EXACT 
COPD Assessment Test (CAT)
 
 Proportion of responders using the CAT at Treatment Days 28, 56, and 84, and following EXACT defined recovery from the index exacerbation Change from baseline (Day 1) in CAT total score at Days 28, 56, and 84 and following EXACT defined recovery from the index exacerbation 
St. George's Respiratory Questionnaire (SGRQ) Total Score
 
 Proportion of responders on the SGRQ total score as measured by the SGRQ for COPD Patients (SGRQ-C) at Days 28, 56, and 84 Change from baseline (Day 1) in SGRQ total score at Days 28, 56, and 84 Rescue medication use (occasions/day), averaged over each week of treatment and over the 84-day treatment period The percentage of rescue-free days (24-

Objectives	Endpoints

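### Section 9.1.1 gives a single, post-bronchodilator baseline FEV₁, which does not fit the secondary endpoints of pre-bronchodilator change from baseline

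*Protocol*

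**What the plan says.** The only baseline statement in the general spirometry section (Section 9.1.1) is "Baseline Clinic Visit FEV₁ is defined as the post-bronchodilator FEV₁ performed at Visit 2". It follows text that covers both pre- and post-bronchodilator testing, and it carries no restriction to one endpoint. The synopsis and Section 4 give the same definition beside the primary endpoint: "Baseline is defined as the post-bronchodilator FEV₁ measured prior to the first dose of double-blind study treatment on Day 1". There it fits, because the primary endpoint is post-bronchodilator at both time points.

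The secondary endpoints in Section 4 include "Change from baseline in Clinic Visit trough FEV₁ measured pre and post-bronchodilator at Days 14, 28, 56, and 84", and also at hospital discharge for participants hospitalized for the index event. For Day 84 the same entry adds that "pre-bronchodilator is a secondary endpoint".

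Both readings are planned at Visit 2. Section 9.1.1 says that "spirometry will be performed prior to administering double-blind study medication at two time points: pre-bronchodilator (albuterol [salbutamol]) and post-bronchodilator", and footnote 5 of the Schedule of Activities agrees. Section 9.1.1 also expects routine albuterol during Visit 2 and says that in this case "spirometry should be scheduled to coincide with this treatment to allow post-bronchodilator recordings to be measured".

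**The concern.** One phrase, change from baseline, governs both the pre- and the post-bronchodilator endpoints, and the only Day 1 baseline the protocol defines is post-bronchodilator. Where another reference is meant, the protocol names it, as in "Change from hospital discharge in clinic visit trough FEV₁ measured pre- and post-bronchodilator at Days, 14, 28, 56, and 84" and in the follow-up endpoints referenced to Day 84. The pre-bronchodilator endpoints referenced to Day 1 have no such override.

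Read literally, a visit value taken before bronchodilator is compared with a baseline taken after it. The result mixes the change over time with the acute response to albuterol at Visit 2. At stake are the reported within-arm changes for this group of secondary endpoints, and how they read beside the post-bronchodilator changes.

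**Working it through.** The protocol gives no figure that depends on this definition, so there is nothing to reproduce. The check is algebra with illustrative numbers.

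**Inputs from the protocol (Section 10.1.1)**
- Between-participant SD of FEV₁: 300 mL at both time points, with correlation 0.7.
- Table 3, Scenario 1 mean change: −20 mL on placebo and +80 mL on 750 mcg. The protocol sets these for the primary endpoint; carrying them over to the pre-bronchodilator endpoint is an assumption.

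**Inputs not in the protocol (assumed)**
- R, the Visit 2 bronchodilator response (post minus pre): mean 50 to 150 mL.
- Participant-level SD of R: 100 mL, independent of the other terms.

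**Shift in the mean**

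(pre-BD at Day t − post-BD baseline) = (pre-BD at Day t − pre-BD baseline) − R

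| Mean R (mL) | Placebo, as written | 750 mcg, as written | Difference |
|---|---|---|---|
| 0 (matched baseline) | −20 | +80 | 100 |
| 50 | −20 − 50 = −70 | 80 − 50 = +30 | 100 |
| 100 | −20 − 100 = −120 | 80 − 100 = −20 | 100 |
| 150 | −20 − 150 = −170 | 80 − 150 = −70 | 100 |

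R is measured before randomized treatment, so its mean is the same in every arm in expectation and cancels from the contrast with placebo. Under these values the 750 mcg mean turns negative only if R exceeds 80 mL.

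**Precision**
- Matched baseline: SD of change = 300 × √(2 × (1 − 0.70)) = 232 mL.
- Mismatched, with the assumed SD of R: √(232.4² + 100²) = 253 mL. A simulation with the same inputs gave 253 mL.
- Mismatched, taking instead an assumed cross-measure correlation of 0.65: 300 × √(2 × (1 − 0.65)) = 251 mL, and 251/232 = 1.08.
- With baseline as a covariate and the same 0.65: 300 × √(1 − 0.65²) = 228 mL against 300 × √(1 − 0.70²) = 214 mL, a ratio of 1.06.

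The direction is plausible. The size rests on inputs that the protocol does not supply.

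**The case against.** The strongest reply is that context limits the definition. In the synopsis and Section 4 it sits with the primary endpoint, where it is right. Section 9.1.1 is a procedural section, and Section 10.3.1 describes no pre-bronchodilator analysis and sends full details to the analysis plan. Paired readings are scheduled at Visit 2, so a careful analyst would probably use the matched value. This is fair, and it keeps the point small. It does not remove it: the protocol did not leave the baseline open but fixed it in general terms, and an analysis plan with a matched baseline would depart from Section 9.1.1 as worded.

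Three stronger readings are tempting, and the documents support none of them.
- A reader might infer that these endpoints will show a false decline. That depends on R, which the protocol does not give. In the example, 750 mcg still shows +30 mL at R = 50 mL.
- A reader might set the shift against the 75 mL in Section 10.1.1. That figure is a difference from placebo, whereas the shift acts within arms and cancels from that difference.
- A reader might take the 8% loss of precision as established. It comes from an assumed correlation of 0.65, and it is nearer 6% with baseline adjustment.

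A further objection stands in part: the matched baseline may not always be clean. Participants are expected to receive routine albuterol at Visit 2, the text on coordinating spirometry with it secures only the post-bronchodilator recording, and Sections 6.3.4 and 9.1.1 ask for withholding only where possible. Some Visit 2 pre-bronchodilator values may be missing or affected.

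**Conclusion.** The point holds as a mismatch between a stated definition and one group of secondary endpoints. As written, each within-arm pre-bronchodilator mean change from Day 1, including the one at hospital discharge, is lowered by the mean Visit 2 bronchodilator response: 50 to 150 mL if that range is assumed. Precision may fall somewhat, by an amount the protocol does not allow to be fixed.

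The comparison with placebo, which is what the secondary objective asks for, stays unbiased in expectation. No success criterion or sample-size figure rests on these endpoints, and the primary endpoint uses post-bronchodilator values on both sides. The endpoints that name discharge or Day 84 as their reference are outside the point. It merits correction because the reported arm means would otherwise be hard to interpret, but it does not threaten the trial's main conclusions.

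**What to change.** In Section 9.1.1, limit the present sentence to post-bronchodilator endpoints. Add that, for pre-bronchodilator endpoints, baseline is the pre-bronchodilator FEV₁ at Visit 2 before the first dose of double-blind treatment. Put the same pair of definitions beside the secondary FEV₁ endpoints in Section 4 and the synopsis.

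State also how the analysis treats a Visit 2 pre-bronchodilator reading that is missing or was taken after routine albuterol, so that this is settled before unblinding.

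The cost is a few sentences. No assessment is added, because the pre-bronchodilator reading is already scheduled at Visit 2. The small downside is that some participants will lack a usable baseline for these secondary endpoints.

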9.1.2. COPD Exacerbation

Following recovery of the index exacerbation, COPD exacerbation assessments will be performed throughout the 12-week treatment period and the 12-week post treatment follow up period at study visits and using the eDiary data.

Additional details on guidelines for COPD exacerbation identification, categorization, reporting and treatment are provided in Section [12.9.5](#).

9.1.3. Patient-Reported Outcomes (PRO)

Participants will complete the following PROs during this study:

- Exacerbations of Chronic Pulmonary Disease Tool (EXACT-PRO) (which includes the Evaluating Respiratory Symptoms in COPD [E-RS: COPD] subscales of the EXACT-PRO) at randomization and every evening following day of randomization,
- St. George's Respiratory Questionnaire for COPD Patients (SGRQ-C) as defined in the SOA (Section [2](#)).
- COPD Assessment Test (CAT) as defined in the SOA (Section [2](#)). CAT will also be triggered to appear in the e-dairy on the evening following EXACT-defined recovery from the index acute moderate or severe exacerbation of COPD.

For participants who are hospitalized, if a participant is too ill to complete the PRO questionnaires without assistance on a given day, a member of the study staff may verbally recite the questions verbatim to the participant and the staff member may enter the participant's verbal response in the eDiary. The participant's confirmation of the accuracy of the staff member's transcription will be documented in the source document/eDiary. Hospitalized participants will be encouraged to complete the eDiary personally as soon as possible and will be trained to do so before discharge.

9.1.3.1. EXAcerbations of Chronic Pulmonary Disease Tool Patient (EXACT-PRO and Evaluating Respiratory Symptoms in COPD (E-RS: COPD)

The Exacerbations of Chronic Pulmonary Disease Tool (EXACT-PRO) is a 14-item, PRO instrument designed to capture information on the occurrence, frequency, severity, and duration of exacerbations of disease in patients with COPD. EXACT-PRO captures information on the severity of the respiratory and systemic manifestations of a COPD exacerbation as reported by the patient [[Leidy, 2011](#)].

The instrument is to be completed every evening (typically at bedtime) using an eDiary. However, at Visit 2 (Randomization) only, the EXACT-PRO is to be completed as the first assessment before randomization and hence will be completed in the morning. Participants will be trained to complete the eDiary before completing the first EXACT assessment.

The daily recording of information allows an assessment of the underlying day to day variability of a patient's symptoms and facilitates the detection of symptom worsening indicative of a COPD exacerbation. The total score for EXACT-PRO ranges from 0 – 100. The entire instrument is intended to be completed in about 3 minutes or less (typically the time required for completion decreases as the patient becomes more familiar with the tool and the eDiary).

The Evaluating Respiratory Symptoms in COPD (E-RS: COPD) consists of 11 items from the 14-item EXACT-PRO instrument. E-RS: COPD is intended to capture information related to the respiratory symptoms of COPD, i.e., breathlessness, cough, sputum production, chest congestion and chest tightness. The E-RS has a scoring range of 0-40 [Leidy, 2014].

Three subscales of the E-RS: COPD are used to describe different symptoms; dyspnoea, cough and sputum and chest symptoms.

Additional details are provided in the SRM/vendor manual.

In addition to the collection of EXACT-PRO, subjects will also complete daily diary questions to provide the information on other symptoms suggestive of exacerbation: sputum purulence (color), wheezing, sore throat, colds (nasal discharge and/or nasal congestion) and fever without other cause.

9.1.3.2. COPD Assessment Test (CAT)

COPD-related health status will be assessed using the CAT at the visits noted in the SoA (Section 2). The CAT will be administered on the eDiary.

Participants will complete the CAT at relevant study visits, prior to performing any other study procedures (including concurrent medication assessment, adverse event assessment, clinic spirometry, etc.), and prior to completion of the SGRQ-C.

The CAT (www.CATestonline.org) is a validated, short and simple patient-completed questionnaire, which has been developed for use in routine clinical practice to measure the health status of patients with COPD. The CAT is designed to measure overall COPD-related health status for the assessment and long-term follow-up of individual patients.

The CAT is an 8-item questionnaire suitable for completion by all patients diagnosed with COPD. When completing the questionnaire, participants rate their experience on a 6-point scale, ranging from 0 (no impairment) to 5 (maximum impairment) with a scoring range of 0-40 [Jones, 2009; Jones, 2012].

Additional details are provided in the SRM/vendor manual.

9.1.3.3. St. George's Respiratory Questionnaire for COPD Patients (SGRQ-C)

Health-related quality of life will be assessed using the SGRQ-C at the visits noted in the SoA (Section 2). The SGRQ-C will be administered on the eDiary.

Participants will complete the SGRQ-C at relevant study visits, prior to performing any other study procedures (including concurrent medication assessment, adverse event assessment, clinic spirometry, etc.), but after completion of the CAT.

The SGRQ-C is a COPD-specific questionnaire designed to measure the impact of COPD and its treatment on the subject's health-related quality of life [Meguro, 2006]. As well as producing an overall summary score, scores for the individual domains of symptoms, activity and impacts are also produced. It has been used in studies of COPD subjects and has been translated and validated for use in most major languages. The SGRQ-C is derived from the original SGRQ, and produces scores equivalent to the SGRQ instrument [Meguro, 2006]. Research has demonstrated that it is sensitive to change and interpretation of the results has been enhanced by determination of the score change necessary to achieve a clinically meaningful improvement in quality of life [Jones, 2005].

The SGRQ-C is self-completed by participants. It is recommended that the SGRQ-C should be conducted at the same time during each applicable visit (see the SoA [Section 2]). Adequate time (at least 20 minutes) should be allowed, although the participant will not be given any stated or implied time limit for completing the questionnaire. The investigator/designee will ask the participant to complete the questionnaire as accurately as possible. If the participant requests help or clarification of any question in the questionnaire, the investigator/designee is to instruct the participant to re-read the instructions to give the best answer possible. The investigator/designee will not supply the participant with an answer to any question.

Additional details are provided in the SRM/vendor manual.

9.1.3.4. Rescue Medication Use

Participants' use of study-supplied rescue medication (albuterol [salbutamol]) will be captured via the clip-on Propeller Sensor for MDI (for countries where the Propeller Sensor for MDI is available) or via the eDiary (for countries where the Propeller Sensor for MDI is not available or for participants who are supplied nebulized albuterol [salbutamol]). For the nebulized formulation, the number of nebulized treatments over the previous 24 hours will be recorded daily in the eDiary.

For participants who are hospitalized and the clip-on Propeller Sensor for MDI is not available and/or if the participant is too ill to complete the eDiary on his/her own on a given day, a member of the study staff may enter the participant's use of non-nebulized rescue medication or the number of nebulized treatments over the previous 24 hours in the eDiary as applicable. The participant's confirmation of the accuracy of the staff member's transcription will be documented in the eDiary/source document. Additional details are provided in the SRM/vendor manual.

9.2. Adverse Events

The definitions of an AE or SAE can be found in [Appendix 4](#).

The investigator and any designees are responsible for detecting, documenting, and reporting events that meet the definition of an AE or SAE and remain responsible for following up AEs that are serious, considered related to the study treatment or the study, or that caused the participant to discontinue the study treatment or study (see Section 8).

9.2.1. Time Period and Frequency for Collecting AE and SAE Information

- All SAEs will be collected from the start of study treatment until Visit 9 in the Post-Treatment Follow-Up Period, at the time points specified in the SoA (Section 2). However, any SAEs assessed as related to study participation (e.g., study intervention, protocol-mandated procedures, invasive tests, or change in existing therapy) or related to a GSK product will be recorded from the time a subject consents to participate in the study.
- All AEs will be collected from the start of double-blind study treatment until Visit 9 in the Post-Treatment Follow-Up Period at the time points specified in the SoA (Section 2).
- Medical occurrences that begin before the start of study treatment but after obtaining informed consent will be recorded on the Medical History/Current Medical Conditions section of the eCRF not the AE section.
- All SAEs will be recorded and reported to the sponsor or designee as soon as possible and not more than 24 hours, as indicated in [Appendix 4](#). The investigator will submit any updated SAE data to the sponsor within 24 hours of it being available.
- Investigators are not obligated to actively seek AEs or SAEs in former study participants. However, if the investigator learns of any SAE, including a death, at any time after a participant has been discharged from the study, and he/she considers the event to be reasonably related to the study treatment or study participation, the investigator must promptly notify the sponsor.
- The method of recording, evaluating, and assessing causality of AEs and SAEs and the procedures for completing and transmitting SAE reports are provided in [Appendix 4](#).

9.2.2. Method of Detecting AEs and SAEs

Care will be taken not to introduce bias when detecting AE and/or SAE. Open-ended and non-leading verbal questioning of the participant is the preferred method to inquire about AE occurrence.

